PROTOCOL TITLE: Evaluation of Software Generated Customized Foot Orthoses

Title: [1771535-1] Evaluation of Software Generated Customized Foot Orthoses

Protocol Version Date: 24 August 2021

1) Objectives

Purpose of the Study:

The purpose of this study is to determine whether custom-made foot orthoses generate a significant decrease in the perception of pain among individuals with foot pain and/or pathology.

Secondary:

1. To determine whether custom-made foot orthoses generate a significant increase in comfort among individuals with foot pain and/or pathology.
2. To determine whether custom-made foot orthoses improve quality of life among individuals with foot pain and/or pathology.

2) Background

Foot orthoses, or orthotics, are prefabricated or custom-made devices that are inserted into shoes to alleviate load and provide cushioning of feet. Prefabricated foot orthoses are also known as “over-the-counter” orthotics and are mass-produced. Custom-made foot orthoses are contoured to an individual’s feet [1].

In general, literature has not been consistent in determining the ideal way in which foot orthoses should be customized and fabricated. Results of studies comparing the effectiveness of prefabricated versus customized foot orthoses show very heterogeneous results, created a large gap in literature. Thus, the current evidence on this subject is quite limited, especially when analyzing the effects of foot orthoses in people without pathologies, since evidence in this group is even scarcer [2, 3].

Foot orthoses have proven to be useful in pain management [4, 5, 6, 7], in non-contact injuries [8, 9] and in overuse pathologies in distal and proximal segments of the lower extremities, as well as in their prevention [10, 11, 12]. In a study that assessed pain in patients with rheumatoid arthritis and forefoot pain, the use of custom-made foot orthoses significantly decreased forefoot pain while walking [13]. In another study comparing custom and non-custom-made foot orthoses, forefoot pain was found to be better relieved by custom-made orthoses than the standard ones [14]. Custom-made foot orthoses can be tailored to specific foot pathologies, as in pain reduction due to the increase in soles pressures in patients affected by rheumatoid arthritis, hallux abductus valgus and secondary metatarsalgia [7]. Custom-made foot orthoses were also useful in shifting pressure

PROTOCOL TITLE: Evaluation of Software Generated Customized Foot Orthoses

off painful areas in patients with intermetatarsal bursitis, reducing pain and disability, which was supported by ultrasound findings [15].

The literature has been consistent in pointing out the positive effects of foot orthoses on comfort in the short term. For example, studies such as that of Tarrade et al [16] found significant improvements in the pain of workers who remained standing for long periods of time when using foot orthoses. However, the medium to long term evidence for this is still not very clear. Among the scarce evidence on this subject, García-Hernández et al. [17] demonstrated that manufacturing workers showed greater comfort after a period of adaptation, which occurred between one and two months after starting the use of foot orthoses. Carrying out this process, using modern, tailor-made manufacturing systems could mean better results, as these methods have proven to be the most effective in generating foot orthoses.

Though the shape of people's feet varies from person to person, currently typical shoes have inside standard foot orthoses that do not provide customized designs to fit the differences in shape of the foot of each person who uses them. This generates a wide range of loading and pressure distribution along the sole. This can generate pain and a reduced quality of life in the people who use them. Today we have the possibility of designing foot orthoses tailored to each person's foot, which generates a support and impacts absorption according to the shape of one's foot, which would allow us to generate greater comfort and thus avoid discomfort and injuries caused by the alteration of the loads. The goal of this study is to find out whether the use of software generated custom-made orthopedic foot orthoses improves pain in the long term.

3) Inclusion and Exclusion Criteria

The attending orthopaedic foot and ankle surgeons will identify patients based on clinical exam and/or radiographic findings. Screening and eligibility will be conducted by the research coordinator.

Inclusion Criteria:

1. Foot/ankle pain or pathology OR diagnosed pes planus, pes cavus, pronator foot, supinator foot, metatarsalgia, Morton's neuroma, sesamoiditis, hallux valgus, intermetatarsal bursitis.
2. Between 18 and 65 years of age
3. BMI is greater than 18.5 or less than 30.

Exclusion Criteria:

1. Individuals who have had surgery in the lower limbs during this past year.
2. Individuals who already have custom-made orthopedic orthoses.
3. Patients with active diabetic ulcers or chronic foot pressure ulcers.

4) Study Timelines

We aim to enroll up to 60 participants over the course of 1-3 months. Each participant will be evaluated at baseline, when the customized foot

PROTOCOL TITLE: Evaluation of Software Generated Customized Foot Orthoses

orthoses will be made, and the corresponding tests will be conducted. Subsequently, consecutive surveys will be carried out at 0, 7, 30, 120, and 360 days. days from the first day of foot orthoses use to measure the change in pain and comfort with use of the foot orthoses. An interim analysis will be conducted after all subjects have completed the 30-day time point. This interim analysis will allow us to determine whether subjects are using the foot orthoses they have been provided. Complete primary analyses is estimated to be completed within 3 months after the termination of the study.

5) Study Endpoints

Primary endpoint: Successful patient use of a 3D printed custom orthotic for at least 6 months and up to 1 year

6) Secondary endpoint: Improvement in patient report outcomes after the use of a 3D printed custom orthoticProcedures Involved

The evaluation will have a duration of approximately 30 minutes, which consists of four stages:

- a. Collection of personal data and anamnesis: The patient's demographic data, anthropometric measurements and anamnesis will be consulted.
- b. Physical examination: Visual and palpitory inspection of the foot.
- c. Baropodometry: Taking of plantar pressures by means of a platform.
 - i. Static: Subjects should remain standing on the platform measuring plantar pressures for 15 seconds with arms at the sides and looking straight ahead. There is only 1 sample.
 - ii. Dynamic:
 1. Walking: Subjects should walk over the pressure measurement platform. Five shots per foot, with a protocol of 5 steps to reach the platform.
- d. Hindfoot photography: A photograph of the hindfoot will be taken, which allows us to measure the angulation of the hindfoot.

Making and Delivery of Foot Orthoses:

During a period of 2 weeks, the foot orthoses will be created using Soleit software which will later be manufactured via three-dimensional printing.

Use of Foot Orthoses:

Foot orthoses will be sent to participants along with a small instruction manual and protocol of use. When using the foot orthoses for the first

PROTOCOL TITLE: Evaluation of Software Generated Customized Foot Orthoses

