I understand that if this study involves use of UC Davis students' educational records (including records in the PI's own possession such as course exams/assignments), I must consult with the Registrar's office to see if all requirements of the Family Educational Rights and Privacy Act (FERPA) are satisfied.

Data Analysis & Statistical Considerations:

PROTOCOL TITLE: Evaluation of Software Generated Customized Foot Orthoses

A quasi-experimental, within-subject (repeated measures) and longitudinal controlled design will be established. Patients will be recruited from the patient population at the University of California, Davis Orthopaedic Foot and Ankle Clinic. From the total number of enrolled subjects who meet the inclusion criteria, an optimal N of 52 subjects will be randomly selected, considering a medium effect size (0.4) and a p less than 0.05 to achieve a statistical power of 0.8. Being a longitudinal study, a sample loss of 10% was established. Therefore, 60 subjects will be included in the study. We aim to enroll up to 60 participants over the course of 1-3 months.

Intra-subject pain, comfort, and quality of life averages pre-use and post use of the foot orthoses will be compared. The sample of participants will be described with central tendency statistics and baseline parameters, and post use evaluations (0, 7, and 30, 120, and 360 days after first foot orthoses use) will be established. These will be compared to study possible differences. For normally distributed dataions, repeated measures, one-way ANOVA for paired samples will be used for normal distributions will be used with a Tukey's post-test and in case of non-normal distributions, Friedman's test will be used with a Dunn's post-test. All analyses will be performed with the SPSS statistical package.

Privacy, Data Storage & Confidentiality:

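### Inclusion criterion 1 sets no symptom duration, so recent self-limiting complaints can enter and their natural recovery would count as orthosis benefit in the uncontrolled pain, comfort and quality-of-life comparisons

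*Protocol*

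**What the plan says.** Protocol section 3 (Inclusion and Exclusion Criteria) gives the condition for entry as "Foot/ankle pain or pathology OR diagnosed pes planus, pes cavus, pronator foot, supinator foot, metatarsalgia, Morton's neuroma, sesamoiditis, hallux valgus, intermetatarsal bursitis". The other two inclusion criteria concern age and BMI. The three exclusions are "Individuals who have had surgery in the lower limbs during this past year", "Individuals who already have custom-made orthopedic orthoses" and "Patients with active diabetic ulcers or chronic foot pressure ulcers". On selection, the section says: "The attending orthopaedic foot and ankle surgeons will identify patients based on clinical exam and/or radiographic findings". No symptom duration, chronicity or minimum pain score appears anywhere.

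Section 1 (Objectives) states the purpose as to "determine whether custom-made foot orthoses generate a significant decrease in the perception of pain among individuals with foot pain and/or pathology". Section 2 (Background) sets the goal as learning whether the use of software-generated "custom-made orthopedic foot orthoses improves pain in the long term". Section 5 names sustained use of the orthotic as the primary endpoint and improvement in patient-reported outcomes as the secondary one.

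The Data Analysis & Statistical Considerations text says: "Intra-subject pain, comfort, and quality of life averages pre-use and post use of the foot orthoses will be compared". Surveys run at days 0, 7, 30, 120 and 360 of use. The design is called controlled, but no comparator group, run-in or repeated baseline is described.

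**The concern.** On an ordinary reading, each condition named after OR is a foot condition that the words before OR already admit, so the list does no work. A recent sprain, contusion or stress injury qualifies as foot or ankle pain. None of the exclusions removes it unless it was operated on in the past year.

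Such complaints can settle within a 360-day follow-up whether or not an orthosis is worn. A within-subject comparison has nothing against which to set that recovery, so it enters the estimated change in full. At stake are the pain purpose in section 1, the comfort and quality-of-life objectives, and the secondary endpoint in section 5. In a one-group study eligibility is one of the few protections against this kind of error, and here it gives none on duration.

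**Working it through.** **The plan's own figure.** The protocol states an effect size of 0.4, p below 0.05 and power 0.8, giving 52 subjects. A two-sided paired t-test with a standardized change of 0.4 needs exactly 52 (power 0.808). Allowing for 10% loss gives 52/0.90 = 57.8, so 58; the plan's 60 is close. The stated size therefore matches a test of one-group change, which cannot separate recovery from device effect.

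**Model for the size of the bias.** From the protocol: n = 52, alpha 0.05, pain scale 0-10. Assumed, because the protocol gives none of them: a share *q* of recent cases whose pain falls by *D* = 3-4 points unaided, SD of change *s* = 2.0-2.5, no mean change in the others, no device effect, and a two-sided test.

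- Mean change = *qD*
- Variance of change = *s*² + *q*(1 − *q*)*D*²
- Noncentrality = √52 × *qD* / √variance, compared with the critical value 2.008 (t, 51 df)

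Low end at *q* = 10% (*D* = 3, *s* = 2.5): mean fall 0.30; variance 6.25 + 0.09 × 9 = 7.06; SD 2.657; noncentrality 7.211 × 0.30/2.657 = 0.814; chance of a significant decrease 12%.

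High end at *q* = 10% (*D* = 4, *s* = 2.0): mean fall 0.40; variance 4 + 0.09 × 16 = 5.44; SD 2.332; noncentrality 7.211 × 0.40/2.332 = 1.237; chance 23%.

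| Share of recent cases | Spurious mean fall (points) | Paired t, all recovery after day 0 | Paired t, half the recovery before day 0 |
|---|---|---|---|
| 0 | 0 | 2.5% | 2.5% |
| 2% | 0.06-0.08 | 4-5% | about 3% |
| 5% | 0.15-0.20 | 6-9% | 4-5% |
| 10% | 0.30-0.40 | 12-23% | 6-10% |
| 20% | 0.60-0.80 | 33-60% | 13-26% |

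The last column halves *D* in the same formulas; the mean falls shown are for full recovery after day 0. Simulation agrees with the formula to within about 1.5 percentage points.

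**Under the planned test.** The protocol names repeated-measures ANOVA with Tukey comparisons (or Friedman with Dunn), not a single paired t-test. Simulating Tukey over five time points for day 0 against day 360, with full recovery after day 0, gives about 3-10% at a 10% share and 16-45% at 20%. With no recent cases that test gives about 0.3% in the benefit direction. Inflation remains, but the absolute chances are lower. At shares of 2-5% they are about 2% or less, which is below 2.5%.

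**The case against.** Five points can fairly be made against this.

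1. *The cause is the missing comparator, not the criterion.* This stands. A reader might infer that tighter eligibility would remove the bias. It would not: natural course and regression to the mean also operate in long-standing complaints.

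2. *The share of recent cases is assumed.* This stands. Subjects come from a specialist foot and ankle clinic, are identified by surgeons, and wait for a device that takes two weeks to make. Few recent injuries may enter. No written rule keeps them out, however, and the protocol gives no figure either way.

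3. *Some recovery may precede the reference measurement.* This stands in part. The pain scale is listed only among the surveys that begin at day 0 of use, after manufacture, and the clinic evaluation lists none. An earlier baseline is possible, since the analysis text mentions baseline parameters, but it is not documented.

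4. *The same criterion admits structural diagnoses without pain.* This stands. Those subjects cannot improve on the pain scale and pull the mean the other way. A reader might infer that the net result must be inflated; the documents do not settle the net direction.

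5. *A broad population matches the objective.* This also stands. Section 1 targets people with foot pain and/or pathology, so limiting entry to long-standing foot pain alone would drop ankle pain and painless pathology and change the question.

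None of these supplies a protection against counting spontaneous recovery as benefit.

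**Conclusion.** The concern holds in a limited form. As written, criterion 1 lets recent self-limiting complaints in, and the planned comparison would credit their recovery to the orthosis in the pain, comfort and quality-of-life results. The effect depends on case mix, which the protocol does not control. Under the paired t-test assumptions it is slight at a 2-5% share (4-9% against 2.5%) and serious at 20% (33-60%). Both ranges fall if part of the recovery comes before day 0 or if Tukey comparisons are used.

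Two stronger readings are not supported. The first is that a false positive for pain is likely: that needs a share of 20-30% or more, for which the documents give no basis. The second is that the trial's primary result is compromised in the same way: the section 5 primary endpoint is use of the orthotic, which recovery does not inflate as it inflates a fall in pain.

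**What to change.** Record the date of symptom onset at the anamnesis already planned in the clinic evaluation. Prespecify that the pain conclusion must also hold in subjects whose symptoms have lasted longer than a minimum duration, which the investigators fix before any data are seen. Alternatively, add that minimum duration to criterion 1 for subjects who qualify through pain, keeping both foot and ankle and leaving entry by pathology as it is. In either case, reword the criterion so that the diagnosis list has a function, or drop the list.

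The cost is one data field and one or two sentences. The restricted analysis has fewer subjects: if 20% were set aside (an assumption), 52 × 0.8 leaves about 42 and the standard error grows by a factor of about 1/√0.8 = 1.12, so it may have less than the planned power. The eligibility route would slow recruitment somewhat. Since either change only reduces the bias, report the pain, comfort and quality-of-life results as uncontrolled change from baseline, not as an effect of the orthosis.

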A conceived device-related risk is that the foot orthoses cause discomfort. This will be controlled in two ways. The first is that the use of the foot orthoses will be done progressively. This means that participants should use the foot orthoses for 1 hour on the first day, then increase use by 1 hour each day until reaching 4 consecutive hours at which time the foot orthoses can be worn continuously. Any discomfort should be reported to the nurse practitioner in charge and will be reviewed to assess if a new foot orthosis with the appropriate modifications should be made or if the use of the foot orthoses should be discontinued.

Blisters:

Another conceived device-related risk is the generation of blisters due to friction. If a participant is found to experience an area of increased rubbing that could lead to a blister, the participant should discontinue the use of the foot orthoses immediately. In addition, as a part of protocol, participants should inspect the soles of their feet when they finish any type of physical activity and check for any areas of redness as a result of the use of the foot orthoses. If any redness is present, inform the nurse practitioner who will assess if new foot orthoses with the appropriate modifications should be made or if the use of the foot orthoses should be discontinued.

12) Potential Benefits to Subjects

Participants will receive custom-made foot orthoses free of charge. No additional compensation will be received.

13) Sharing of Results with Subjects

N/A Results will not be shared with patients.

14) Provisions to Protect the Privacy Interests of Subjects

As part of the consent process, the patients will be informed about the nature of the data that will be collected, how the information will be collected and who will have access to the information and how it will be stored. The information will be handled initially by the clinical and research team at the collecting institution and only shared with the data hub institution UC Davis in a deidentified format.

15) Economic Burden to Subjects

The only anticipated cost is transportation to the clinic during the initial visit. There will be no cost to the subjects for the manufacturing of the foot orthoses. The non-standard of care foot orthoses will be paid for by Soleit.

16) Drugs or Devices

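### Exclusion 3 removes only patients with an ulcer at present, so patients with known loss of feeling in the feet are eligible, although two of the three warning signs in Section 11 depend wholly or mainly on feeling.

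*Protocol*

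**What the plan says.** **Who may enter (Protocol, Section 3).** There are three exclusions. The first concerns recent operations on the legs or feet, and the second concerns people who own custom orthoses when screened. The third, which matters here, is worded "Patients with active diabetic ulcers or chronic foot pressure ulcers".

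Inclusion 1 begins "Foot/ankle pain or pathology OR diagnosed pes planus, pes cavus, pronator foot" and goes on to list further diagnoses. Attending surgeons identify patients from the clinical examination, radiographs or both. The research coordinator then carries out screening and decides eligibility.

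**What is examined at baseline (Section 6, procedures).** The foot examination is given as "Physical examination: Visual and palpitory inspection of the foot". History taking, plantar pressure measurement and a hindfoot photograph complete the evaluation.

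**How harm is to be limited (Section 11).** For discomfort there are two controls. One is gradual wear: "The first is that the use of the foot orthoses will be done progressively". The other is the participant's own report: "Any discomfort should be reported to the nurse practitioner in charge". For blisters, a participant who experiences rubbing is to stop wearing the orthoses. In addition, "participants should inspect the soles of their feet when they finish any type of physical activity" and should tell the nurse practitioner about any redness.

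**Contact after baseline.** The orthoses are sent to participants and follow-up is by survey (Section 6). The only clinic trip foreseen is the initial visit (Section 15).

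**The concern.** Exclusion 3 recognises that skin breakdown on the foot is a hazard with this device, but it removes only patients in whom breakdown is present now. A patient whose ulcer has healed, or whose record shows loss of feeling in the feet, can be enrolled. Section 11 depends to a large extent on the participant noticing that something is wrong. In a participant who cannot feel the sole, reports of discomfort and rubbing are the signs most likely to fail. That participant may wear the device for up to 360 days, and no member of staff is scheduled to look at the feet in that time.

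The stakes are mainly participant safety in a small subgroup. A lesser matter is that the study's purpose (Section 1) is a reduction in perceived pain, and the ratings of such participants may add little information on it.

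**Working it through.** No arithmetic applies, and the protocol gives no figure to reproduce. The check sets the eligibility text beside the safeguards.

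**Step 1. Can a patient with insensate feet and no current ulcer enter?**

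| Criterion (Section 3) | Keeps this patient out? |
|---|---|
| Inclusion 1 | No. Pathology or a listed diagnosis is enough; pain is not required |
| Inclusion 2 and 3 (age, BMI) | No. Unrelated to sensation |
| Exclusion 1 (recent surgery) | No. Unrelated to sensation |
| Exclusion 2 (existing custom orthoses) | No. Unrelated to sensation |
| Exclusion 3 (ulcers) | No. It covers a present ulcer only |

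Thus 0 of 3 exclusions address sensation or a past ulcer.

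**Step 2. Does another written step catch the patient?** The baseline foot examination is by eye and hand, with no sensory test named. A patient may be identified on radiographs without a clinical examination being decisive. The coordinator who decides eligibility has only the written criteria to apply. A surgeon may well hold such a patient back, but no criterion requires it.

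**Step 3. Which Section 11 measures need sensation?**

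| Measure | Role | Needs the wearer to feel? |
|---|---|---|
| Gradual wear in the first week | Limits exposure | No |
| Reported discomfort | Trigger for review | Yes |
| Rubbing that is experienced | Trigger to stop | Mainly; rubbing could also be seen |
| Redness on self-inspection | Trigger for review | No; it is visual |

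Thus 2 of 3 triggers depend wholly or mainly on sensation. The third is carried out by the participant and is tied to the end of physical activity. Gradual wear is a further measure that does not need sensation, but it applies only at the start of use.

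**Step 4. Is there a backstop during use?** No visit or staff foot check is scheduled after the initial visit. The day-7 survey asks about tolerance, but it is again self-report. Section 6 records only adverse events that are serious, unexpected and related to the device, so an ordinary blister, which Section 11 names as a foreseen risk, would not be recorded.

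**The case against.** The strongest reply is that exclusion 3 and Section 11 do not contradict each other: the sponsor drew a narrower exclusion than a reviewer might, in a study it classes as minimal risk. Section 11 also holds more than symptom reports. Gradual wear is the first control it names. The sole check follows physical activity of any kind, which could include ordinary walking. There are also the baseline history, examination and pressure measurement, the day-7 tolerance survey and ongoing sponsor monitoring (Section 9). The instruction manual sent with the orthoses is not shown and may say more about inspection.

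Much of this stands, and it limits the point. It does not remove it, because none of these layers is a written screen for sensation or a scheduled staff inspection during use.

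A reader might infer several stronger things that the protocol does not support:

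- *That every safeguard fails without sensation.* It does not: gradual wear and the redness check remain.
- *That gradual wear is over by day 4.* Adding one hour a day from one hour does reach four hours on day 4, but Section 6 also calls the whole first week an adaptation period. The point does not rest on either reading.
- *That these participants cannot rate pain, or that their ratings add noise.* Nothing in the protocol shows either. Inclusion 1 already admits people without pain, so low pain scores would not arise from exclusion 3 alone.
- *That a given share of the 60 participants is affected.* The protocol gives no figure from which to estimate one.

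**Conclusion.** The point holds as a gap between two parts of the protocol. Followed exactly, Section 3 admits patients with known loss of foot sensation or a healed ulcer, and the symptom-based part of Section 11 serves those patients poorly. Protection for them is weakened, not absent.

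The size can be stated only from the text: 0 of 3 exclusions cover the matter, 2 of 3 triggers rely wholly or mainly on feeling, and no staff foot checks are scheduled after the initial visit. The number of participants affected is unknown and may be small. On the study's purpose, the most that can be said is that their pain ratings may add little information.

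The conclusion assumes that eligibility is decided on the written criteria, and that the unseen instruction manual and consent form add no sensory screen or staff inspection. The change is worth making because it is cheap and concerns safety. The planned pain comparison does not depend on it.

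**What to change.** Reconcile the eligibility criteria in Section 3 with the safeguards in Section 11. One way is for the investigators to extend exclusion 3 by a phrase covering documented loss of sensation in the feet or a previous foot ulcer. This would be judged from the medical record, the history taken at baseline and the clinical examination already performed. Because identification may rest on radiographs alone, the record and the history should count as well as the surgeon's examination. No new test is needed, and the rules on wear and stopping stay as they are.

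The cost is one phrase, a few patients fewer, and no claim for patients with insensate feet. If the investigators prefer to keep these patients, the protocol should say so and explain how the Section 11 safeguards are meant to work for them.
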